6. OBJECTIVES

Primary Objective:

- To assess the safety and efficacy of repeated IVT injections of DE-122 (2.0 mg/eye and 4.0 mg/eye) given in combination with Lucentis® in subjects with wet AMD compared with Lucentis® alone.

Secondary Objective:

- To evaluate the pharmacokinetics and immunogenicity of DE-122 following repeated IVT injections of DE-122 in subjects with wet AMD in serum samples.
- To evaluate biomarker candidates of DE-122 following repeated IVT injections of DE-122 in subjects with wet AMD in both serum and aqueous humor samples.

7. INVESTIGATIONAL PLAN

7.1. Overall Study Design and Plan

This is a randomized, double masked and active controlled study assessing the safety and efficacy of repeated intravitreal injections of DE-122 (2.0 mg or 4.0 mg) in combination with Lucentis® compared to Lucentis® monotherapy in subjects with wet AMD. Approximately seventy six (76) subjects with wet AMD will be randomly assigned to one of three treatment arms:

Arm 1: Sham + Lucentis® 0.5 mg (N=17)

Arm 2: DE-122, 2.0 mg + Lucentis® 0.5 mg (N=31)

Arm 3: DE-122, 4.0 mg + Lucentis® 0.5 mg (N=28)

Subjects will receive 6 monthly intravitreal injections of DE-122 (2.0 mg or 4.0 mg) or Sham in the study eye, in combination with Lucentis®.

The first 6 subjects will be randomized to Arm 1 or Arm 2 in a 1:1 ratio in Stage 1. The Safety Review Team will review the safety parameters of the 6 subjects in Stage 1 and determine if the safety and tolerability at Week 4 are acceptable. If so, enrollment will be continued in a 1:2:2 ratio in the three arms for the remaining approximately 70 subjects in Stage 2.

To be eligible, subjects must have a diagnosis of active CNV secondary to AMD, with some subfoveal component (CNV, fluid, or hemorrhage under the fovea) with lesions \leq 12 disc areas and \leq 50% hemorrhage in the study eye. Subjects must be previously treated (i.e., At least 3 IVT injections of Anti-VEGF for treatment naïve eyes or eyes adequately maintained on continuous intravitreal anti-VEGF therapy). Subjects with Polypoidal Choroidal Vasculopathy (PCV) lesions will be allowed, but Retinal Angiomatous Proliferation (RAP) lesions will be excluded from this study.

Screening Visit SD-OCT images and Fluorescein Angiography from Investigator-identified eligible subjects will be sent to the central reading center to confirm eligibility based on AMD lesion attributes specified in the protocol. To balance the randomization, subjects will be stratified by subgroups on the reading center's assessment of lesion type, up to approximately one third (1/3) of the subjects in each arm should have PCV in Stage 2. Subjects must satisfy all other inclusion and exclusion criteria.

Subjects must have best corrected visual acuity (BCVA) of 65 to 25 ETDRS letters (equivalent to 20/50 to 20/320 Snellen) in the study eye.

[figure not shown]
Eligible subjects who are enrolled in the study will be seen for up to 14 visits.

The Primary Analysis is planned when all subjects complete the Week 24 visit. The Follow-up Analysis is planned at Week 32 to assess the number of anti-VEGF injections used for Rescue in addition to efficacy and safety data.

Subjects are eligible for rescue with any anti-VEGF IVT injection during the Week 24 and Week 28 if one of the following rescue criteria is met:

Rescue Criteria:

- BCVA decrease of ≥ 5 letters from the last visit score
- CST increase from the last visit of $\geq 50\mu\text{m}$
- The discretion of investigator

Figure 1: Study Schematic**7.1.1. Selection of Concentrations in the Study**

In this clinical study, two dose levels of DE-122 (2.0 mg and 4.0 mg) are being tested in subjects with wet AMD. The maximum amount of DE-122 that a subject can possibly receive is 24 mg over a 20 week period. Systemic exposure of DE-122 in this study given 6 times by IVT injection is anticipated to be significantly lower than the systemic exposure in over 500 cancer

subjects (most of whom received 10 mg/kg of TRC105 by weekly intravenous infusion). Therefore, no concerns regarding systemic toxicity are anticipated in this study.

In pre-clinical studies, the highest tested DE-122 IVT dose of 5 mg/injection in the monkey eye would correlate to 10 mg/eye in human eyes due to the difference in volume, hence the difference in vitreous volume between human and monkey (2:1 ratio) conveys a margin of safety.

In the mouse model of laser-induced CNV efficacy study, animals were given an IVT injection of DE-122 at 0.5, 1.5 and 5.0 µg/eye. DE-122 inhibited CNV in a dose-dependent manner. The highest effective dose was 5 µg/eye. Considering the vitreous volume difference between human and mouse (~1000:1 ratio), a range of 0.5 to 5 mg/eye is considered a logical effective dose level for humans.

In Phase I/II clinical study (Protocol 36-001), four dose levels of DE-122 (0.5 mg, 1.0 mg, 2.0 mg and 4.0 mg) were tested in subjects with refractory wet AMD. No dose-dependent events were reported and no new safety concerns were identified at all investigated doses. Most common AE was Subconjunctival haemorrhage (3 subjects, 25%) and all were considered to be due to the injection procedure.

7.2. Number of Subjects

Approximately 76 subjects (Arm 1: 17 subjects, Arm 2: 31 subjects, Arm 3: 28 subjects) with wet AMD will be enrolled at approximately 14 sites in the Philippines and the US. The final number of subjects enrolled may be adjusted up to 80 based on drop-out rate.

7.3. Treatment Assignment

Two dose levels of DE-122 and Lucentis® will be administered by IVT injection in the study eye.

- DE-122 injectable solution 2.0 mg (20 µL of 100 mg/mL)
- DE-122 injectable solution 4.0 mg (40 µL of 100 mg/mL)
- Ranibizumab (Lucentis®) 0.5 mg (50 µL of 10 mg/mL)

7.4. Dose Adjustment Criteria

The Safety Review Team will review safety parameters after the 6 subjects in Stage 1 have completed Week 4. If the safety criteria for adjusting or stopping doses and the criteria for study termination are not met, the remaining subjects in three Arms will be enrolled in the study.

7.4.1. Safety Criteria for 6 Subjects in Stage 1

If more than one of the following events is observed by Week 4 visit in Stage 1, planned doses may be adjusted or stopped by the Safety Review Team.

- Visual acuity loss from baseline defined as:
 - Loss of best corrected visual acuity (BCVA) of 30 or more letters not due to vitreous hemorrhage or injection procedure **OR**
 - Transition to no light perception (NLP) not due to injection procedure
- Clinically significant inflammation defined as:

- > 3+ vitreous haze as measured by the National Eye Institute Grading Scheme ([Nussenblatt et al., 1985](#)) **OR**
 - Sterile endophthalmitis (including the presence of hypopyon)
- Severe IOP elevation as measured by tonometry, on two separate exams, at least one day apart, excluding day of injection (despite pharmaceutical intervention):
 - > 35 mmHg **OR**
 - Increase of > 15 mmHg from baseline
- Retinal non-perfusion of the study eye/vascular occlusion
- Vasculitis
- Retinitis
- > 2+ disc edema
- > 2 quadrants of retinal hemorrhage

If there is insufficient safety information in either in the 6 subjects in Stage 1, the Safety Review Team may decide to treat additional subjects before continuing enrollment in the study.

Criteria for Study Termination

Unacceptable safety signals that prevent continuing to other subjects in all arms or result in stopping the study may include any of the following, if deemed to be related to DE-122 study drug (not DE-122 administration procedures):

- Pattern of systemic AEs
- Any of the following AEs in any 2 subjects in any cohort:
 - Retinal non-perfusion of the study eye/vascular occlusion
 - Vasculitis
 - Retinitis
 - > 2+ disc edema
 - > 2 quadrants of retinal hemorrhage

7.5. Study Procedures

All subjects must sign a written ICF before participating in any study-related activity, and the subject will be assigned a unique screening number. Central randomization will occur at Visit 1 (Day 1) after a subject meets all eligibility requirements at Screening. Each randomized subject will be assigned a unique subject number. If a subject is discontinued from the study for any reason, the subject number will remain in effect and will not be reused.

A Schedule of Events can be found below and detailed procedures for examinations can be found in [Section 23.4](#), Appendix D – Procedures for Examinations.

Table 3: Schedule of Events

***Only the subjects who have consented under the protocol prior to Version 4.0 (Amendment 07) require the grayed-out examinations in the table.**

Visit Number	Visit 0 (SCRN)	Visit 1	Visit 2	Visit 3	Visit 4	Visit 5	Visit 6	Visit 7	Visit 8	Visit 9	Visit 10	Visit 11	Visit 12	Visit 13 /Exit
Visit Schedule (Time window; days)	D-14 to -1	D1	D3	W1	W4	W8	W12	W16	W20	W20 + 2 days	W20 + 7 days	W24	W28	W32
			D3	D8 (±1)	D29 (±3)	D57 (±3)	D85 (±4)	D113 (±4)	D141 (±4)	W20 + 2 days	W20 + 7(±1) days	D169 (±5)	D197 (±5)	D225 (±5)
Informed consent ^a	X													
Demographics/Eligibility	X													
Medical/surgical history, Concomitant medication	X	X	X	X	X	X	X	X	X	X	X	X	X	X
Physical examination	X											X		X
Vital signs	X	X		X	X	X	X	X	X			X	X	X
EKG	X			X								X	X	X
BCVA (ETDRS)	X	X		X	X	X	X	X	X			X	X	X
M-CHARTSTM	X	X		X	X	X	X	X	X			X	X	X
Slit-lamp biomicroscopy ^b	X	X		X	X	X	X	X	X			X	X	X
Intraocular pressure (IOP) ^c	X	X		X	X	X	X	X	X			X	X	X
Indirect ophthalmoscopy ^b	X	X		X	X	X	X	X	X			X	X	X
SD-OCT	X	X		X	X	X	X	X	X			X	X	X
SS-OCT angiography ^d	X	X		X	X	X	X	X	X			X	X	X
Fundus photography	X				X		X					X		X
Fluorescein angiography	X				X		X					X		X
Urine pregnancy test ^e		X												
Urinalysis ^f	X				X		X					X		X
Serum pregnancy test ^e	X											X		X
Hematology, chemistry serum sample ^f	X				X		X					X		X
PK serum sample ^g		X	X	X	X					X	X	X	X	

Table 3: Schedule of Events (Continued)

Visit Number	Visit 0 (SCRN)	Visit 1	Visit 2	Visit 3	Visit 4	Visit 5	Visit 6	Visit 7	Visit 8	Visit 9	Visit 10	Visit 11	Visit 12	Visit 13 /Exit
Visit Schedule (Time window; days)	D-14 to -1	D1	D3	W1	W4	W8	W12	W16	W20	W20 + 2 days	W20 + 7 days	W24	W28	W32
			D3	D8 (±1)	D29 (±3)	D57 (±3)	D85 (±4)	D113 (±4)	D141 (±4)	W20 + 2 days	W20 + 7(±1) days	D169 (±5)	D197 (±5)	D225 (±5)
Biomarker serum sample ^g		X	X	X					X	X	X	X		
Immunogenicity serum sample		X										X		
Pharmacogenomics/genomics blood sample ^{a, h}		X												
Biomarker aqueous humor sample ^a		X			X				X					
Lucentis® IVT injection ⁱ		X			X	X	X	X	X					
DE-122 or Sham IVT Injection ⁱ		X			X	X	X	X	X					
Adverse event		X	X	X	X	X	X	X	X	X	X	X	X	X

SCRN= Screening; D=Day; W=Week; PK=Pharmacokinetic

a. Informed Consent - obtain prior to conducting any study-related activities. Separate informed consent is required to participate in the ancillary Biomarker aqueous humor sample collection and Pharmacogenomics/genomics blood sample collection.

b. On days when either Lucentis®/DE-122 or Lucentis®/Sham IVT injections are administered, slit lamp biomicroscopy and indirect ophthalmoscopy will be performed prior to injection and within 30 minutes after DE-122 or Sham injection. This will be also applied for the post IVT injection of Rescue treatment.

c. On days when either Lucentis®/DE-122 or Lucentis®/Sham IVT injections are administered, IOP will be performed before and after Lucentis® IVT injection. In addition, after DE-122 or Sham injection, IOP will be performed again. This will be also applied for the post injection of Rescue treatment.

d. Selected sites will conduct.

e. Serum and urine pregnancy tests are to be performed on all females of child-bearing potential.

f. Subjects should fast for a minimum of 8 hours prior to urine specimen and blood draw for serum chemistry tests.

g. At baseline (Day 1, Visit 1), serum sample for DE-122 concentration (if applicable) and biomarker will be collected

- 1) prior to the Lucentis® injection;
- 2) post DE-122 or Sham injection: 3 hours, 48 hours, 1 week and 4 weeks (prior to the Lucentis® injection).

At Week 20, serum sample for DE-122 concentration (if applicable) and biomarker will also be collected

- 1) prior to the Lucentis® injection;
- 2) post DE-122 or Sham injection: 3 hours, 48 hours, 1 week and 4 weeks.

h. Pharmacogenomics/genomics blood sample can be drawn once at Day 1 or any visit after Visit 1(Day 1) during the study.

i. Lucentis® will be administered first, and then DE-122 or Sham will be injected. Rescue treatment with any anti-VEGF IVT injection can be performed during the Week 24 and Week 28 visits.

7.5.1. Screening Phase

7.5.1.1. Visit 0/Screening (Day -14 to Day -1)

- Explain the purpose and details of the study to the subject and obtain written informed consent prior to the subject's participation in any study related activity.
- Obtain separate informed consent for participant in the ancillary Biomarker aqueous humor sample collection and Pharmacogenomics/genomics blood sample collection. Ensure that the subject understands that if they do not wish to provide aqueous humor sample and blood sample for the Biomarker research study and the Pharmacogenomics/genomics study that it will not affect the subject's enrollment in the trial.
- Obtain subject's demographic information, medical, surgical and medication history.
- Perform the following assessments: (all ophthalmic procedures to be performed OU). The procedures of each assessment are described in [Section 23.4, Appendix D](#).
 - Physical examination (if not performed by external internist)
 - Vital signs
 - EKG
 - BCVA (ETDRS)
 - M-CHARTS™
 - Slit-lamp biomicroscopy
 - IOP
 - Indirect ophthalmoscopy
 - SD-OCT
 - SS-OCT angiography (for selected sites)
 - Fundus photography
 - Fluorescein angiography
- Review the inclusion and exclusion criteria. Do not continue screening any subject who does not meet the screening eligibility requirements.
- If the subject continues to be eligible for the study, collect more than 8 hours fasting urine and blood specimen for the following examinations:
 - Urinalysis
 - Serum pregnancy test (for females of child-bearing potential)
 - Hematology, chemistry serum sample
- If subject has not been fasting, schedule the subject as soon as possible for fasting blood draw and urine specimen.

- Upload collected images (Fluorescein angiography, Fundus photography and SD-OCT) of both eyes to the central reading center for confirmation of subject eligibility.
- Schedule the subject to return for Visit 1 (Day 1).

7.5.2. Treatment/follow-up phase

[figure not shown]
7.5.2.1. Visit 1 (Day 1)

- **Review** results of the following procedures performed at Screening (Day -14 to Day -1) to determine continuation in the study:
 - Physical examination
 - EKG
 - Urinalysis
 - Blood chemistry and hematology tests
 - Serum pregnancy test (for females of child-bearing potential)
 - Eligibility determination by the central reading center
- If the subject continues to be eligible for the study, the following assessments must be performed prior to administration of study drugs to confirm eligibility and obtain baseline characteristics: (all ophthalmic procedures to be performed OU)
 - Query for AEs
 - Update medical history and medications
 - Vital signs
 - BCVA (ETDRS)
 - M-CHARTS™
 - Slit-lamp biomicroscopy
 - IOP
 - Indirect ophthalmoscopy
 - SD-OCT
 - SS-OCT angiography (for selected sites)
- If the subject continues to be eligible for the study, collect urine and blood specimen for the following examinations:
 - Urine pregnancy test (for females of child-bearing potential)
 - PK serum sample (**for only the subjects who have consented under the protocol prior to Version 4.0**)
 - Immunogenicity serum sample

- Biomarker serum sample
- If the subject has consented to the Pharmacogenomics/genomics study, collect blood sample for the Pharmacogenomics/genomics study. Blood collection for the Pharmacogenomics/genomics study can be alternatively collected once at any visit during the study after Visit 1(Day 1).
- Perform final review of inclusion/exclusion criteria. If the subject has met all eligibility criteria, including confirmation of the lesion eligibility by the central reading center (which will also confirm lesion type), determine the study eye. The subject is then randomized, via IWRS.
- After the subject has been randomized to a treatment Arm, Lucentis® will be administered as per drug labeling.
- If the subject has consented to the Biomarker aqueous humor sample collection, collect the aqueous humor sample before Lucentis® administration.
- **Perform Lucentis® administration** as per drug labeling, and then perform the following procedures after Lucentis® administration.
 - IOP will be measured at 40 (± 10) minutes post-injection.
 - If post-injection IOP is ≤ 21 mmHg AND increased < 10 mmHg from pre-injection IOP and there is no concern regarding retinal artery perfusion, DE-122 or Sham IVT will be administered.
 - If post-injection IOP is > 21 mmHg OR increased ≥ 10 mmHg from pre-injection IOP, IOP measurement will be repeated at 60 (± 10) minutes post-injection.
 - IOP will be measured at 60 (± 10) minutes post-injection, if applicable.
 - If post-injection IOP at 60 (± 10) minutes is ≤ 21 mmHg AND increased < 10 mmHg from pre-injection IOP and there is no concern regarding retinal artery perfusion, DE-122 or Sham IVT will be administered.
 - If post-injection IOP at 60 (± 10) minutes is > 21 mmHg, however the IOP is < 30 mmHg AND increased < 10 mmHg from pre-injection IOP and there is no concern regarding retinal artery perfusion, DE-122 or Sham IVT will be administered per the Clinical Investigator's discretion.
If the Clinical Investigator determine that DE-122 or Sham IVT will Not be administered, the subject will be treated according to the Clinical Investigator's discretion. In addition, the Clinical Investigator has the discretion on whether to have the subject continue or exit the study.
 - **If post-injection IOP at 60 (± 10) minutes is ≥ 30 mmHg OR increased ≥ 10 mmHg from pre-injection IOP, DE-122 or Sham IVT will not be administered.** The subject should be prescribed a topical IOP-lowering medication until he or she returns for follow-up per the Clinical Investigator's discretion (an unscheduled visit may apply), and the event will be reported as

an AE. In addition, the Clinical Investigator has the discretion on whether to have the subject continue or exit the study.

- **Perform DE-122 or Sham administration**, and then perform the following procedures after DE-122 or Sham administration.
- After DE-122 or Sham administration, the following will be performed: (all ophthalmic procedures to be performed OU)
 - Within 30 minutes following DE-122 or Sham IVT
 - Slit-lamp biomicroscopy
 - Indirect ophthalmoscopy
 - IOP measurement 40 (± 10) minutes following DE-122 or Sham IVT injection
 - If post-DE-122 or Sham injection IOP is > 21 mmHg OR increased ≥ 10 mmHg from pre-Lucentis[®] injection, IOP measurement will be repeated at 60 (± 10) minutes post-injection.
 - IOP will be measured at 60 (± 10) minutes following DE-122 or Sham IVT injection, if applicable.
 - If post-DE-122 or Sham injection IOP at 60 (± 10) minutes is ≥ 30 mmHg OR increased ≥ 10 mmHg from pre-Lucentis[®] injection IOP, the subject should be prescribed a topical IOP-lowering medication, and the IOP elevation will be reported as an AE. Per the Clinical Investigator's discretion, the subject can return for follow-up (an unscheduled visit may apply).
 - If post-DE-122 or Sham injection IOP at 60 (± 10) minutes is > 21 mmHg AND < 30 mmHg, the subject will be treated according to the Clinical Investigator's discretion.
- AE assessments must be performed after each IVT injection.
- Collect blood specimen for the following examinations at 3 hrs (± 10 mins) post DE-122 or Sham injection. If DE-122 or Sham IVT injection is skipped, the blood sampling will be done at 3 hrs (± 10 mins) post Lucentis[®] administration.
 - PK serum sample (**for only the subjects who have consented under the protocol prior to Version 4.0**)
 - Biomarker serum sample
- Upload collected images (SD-OCT) of the study eye to the central reading center.
- Schedule the subject to return for Visit 2 (Day 3) or Visit 3 (Week 1 (D8 \pm 1)).

7.5.2.2. Visit 2 (Day 3)

For only the subjects who have consented under the protocol prior to Version 4.0

- Perform the following assessments:
 - Query for AEs
 - Update medical history and medications
- Collect blood specimen for the following examinations at 48 (± 2) hrs post DE-122 or Sham injection. If DE-122 or Sham IVT injection was skipped at Visit 1, blood specimen will be collected at 48 (± 2) hrs post Lucentis[®] IVT injection.
 - PK serum sample
 - Biomarker serum sample
- Schedule the subject to return for Visit 3 (Week 1 (D8 ± 1)).

7.5.2.3. Visit 3 (Week 1 (D8 ± 1))

[figure not shown]
- Perform the following assessments: (all ophthalmic procedures to be performed OU)
 - Query for AEs
 - Update medical history and medications
 - Vital signs
 - EKG
 - BCVA (ETDRS)
 - M-CHARTSTM
 - Slit-lamp biomicroscopy
 - IOP
 - Indirect ophthalmoscopy
 - SD-OCT
 - SS-OCT angiography (for selected sites)
- Collect blood specimen for the following examinations:
 - PK serum sample (**for only the subjects who have consented under the protocol prior to Version 4.0**)
 - Biomarker serum sample
- Upload collected images (SD-OCT) of the study eye to the central reading center.
- Schedule the subject to return for Visit 4 (Week 4 (D29 ± 3)). Remind subjects to fast 8 hours prior to next visit.

7.5.2.4. Visit 4 (Week 4 (D29±3))

- Perform the following assessments: (all ophthalmic procedures to be performed OU)
 - Query for AEs
 - Update medical history and medications
 - Vital signs
 - BCVA (ETDRS)
 - M-CHARTS™
 - Slit-lamp biomicroscopy
 - IOP
 - Indirect ophthalmoscopy
 - SD-OCT
 - SS-OCT angiography (for selected sites)
 - Fundus photography
 - Fluorescein angiography
- Collect urine and blood specimen for the following examinations:
 - Urinalysis
 - Hematology, chemistry serum sample
 - PK serum sample (**for only the subjects who have consented under the protocol prior to Version 4.0**)
 - Biomarker serum sample
- **Perform Lucentis® administration** as per drug labeling, and then perform the following procedures after Lucentis® administration.
 - IOP will be measured at 40 (± 10) minutes post-injection.
 - If post-injection IOP is ≤ 21 mmHg AND increased < 10 mmHg from pre-injection IOP and there is no concern regarding retinal artery perfusion, DE-122 or Sham IVT will be administered.
 - If post-injection IOP is > 21 mmHg OR increased ≥ 10 mmHg from pre-injection IOP, IOP measurement will be repeated at 60 (± 10) minutes post-injection.
 - IOP will be measured at 60 (± 10) minutes post-injection, if applicable.
 - If post-injection IOP at 60 (± 10) minutes is ≤ 21 mmHg AND increased < 10 mmHg from pre-injection IOP and there is no concern regarding retinal artery perfusion, DE-122 or Sham IVT will be administered.

- If post-injection IOP at 60 (± 10) minutes is > 21 mmHg, however the IOP is < 30 mmHg AND increased < 10 mmHg from pre-injection IOP and there is no concern regarding retinal artery perfusion, DE-122 or Sham IVT will be administered per the Clinical Investigator's discretion.
If the Clinical Investigator determine that DE-122 or Sham IVT will Not be administered, the subject will be treated according to the Clinical Investigator's discretion.
- **If post-injection IOP at 60 (± 10) minutes is ≥ 30 mmHg OR increased ≥ 10 mmHg from pre-injection IOP, DE-122 or Sham IVT should not be administered.** The subject should be prescribed a topical IOP-lowering medication until he or she returns for follow-up per the Clinical Investigator's discretion (an unscheduled visit may apply), and the event will be reported as an AE.
- **Perform DE-122 or Sham administration**, and then perform the following procedures after DE-122 or Sham administration.
- After DE-122 or Sham administration, the following will be performed: (all ophthalmic procedures to be performed OU).
 - Within 30 minutes following DE-122 or Sham IVT
 - Slit-lamp biomicroscopy
 - Indirect ophthalmoscopy
 - IOP measurement 40 (± 10) minutes following DE-122 or Sham IVT injection
 - If post-DE-122 or Sham injection IOP is > 21 mmHg OR increased ≥ 10 mmHg from pre-Lucentis[®] injection, IOP measurement will be repeated at 60 (± 10) minutes post-injection.
 - IOP will be measured at 60 (± 10) minutes following DE-122 or Sham IVT injection, if applicable.
 - If post-DE-122 or Sham injection IOP at 60 (± 10) minutes is ≥ 30 mmHg OR increased ≥ 10 mmHg from pre-Lucentis[®] injection IOP, the subject should be prescribed a topical IOP-lowering medication, and the IOP elevation will be reported as an AE. Per the Clinical Investigator's discretion, the subject can return for follow-up (an unscheduled visit may apply).
 - If post-DE-122 or Sham injection IOP at 60 (± 10) minutes is > 21 mmHg AND < 30 mmHg, the subject will be treated according to the Clinical Investigator's discretion.
- AE assessments must be performed after each IVT injection.
- If the subject has consented to Biomarker aqueous humor sample collection, collect the aqueous humor sample after DE-122 or Sham IVT. If DE-122 or Sham IVT is not administered, the aqueous humor sample should be collected with no time restriction.

- If subject has not been fasting, schedule the subject as soon as possible for fasting blood draw and urine specimen.
- Upload collected images (Fluorescein angiography, Fundus photography and SD-OCT) of the study eye to the central reading center.
- Schedule the subject to return for Visit 5 (Week 8 (D57±3)).

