23.4.21. Procedure for Biomarker Aqueous Humor Sample

Approximately 50~120 μ L of aqueous humor sample will be collected for biomarker analysis from the subject at Visit 1 (Day 1), Visit 4 (Week 4) and Visit 8 (Week 20).

Refer to the separate procedure manual for sample handling, storage, and shipment.

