## 12. BIOMARKER ANALYSIS

Translational Research will provide the report of biomarker investigation. Scores, changes from baseline and percent change from baseline in levels of potential biomarkers will be summarized descriptively by actual treatment received and analysis visit. Besides the summary tables, plots of biomarker measures versus analysis visit will be provided. Pearson's correlation between change from baseline in BCVA and each biomarker will be analyzed by actual treatment and analysis visit. The 95% confidence interval of the correlation coefficient based on Fisher's Z transformation will be provided.

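### Aqueous biomarkers are sampled before any injection at Day 1 but after injection at Weeks 4 and 20, so the planned change from baseline mixes the injection given at that visit with earlier treatment

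*Protocol*

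**What the plan says.** Aqueous humor is scheduled at three visits only: Day 1, Week 4 and Week 20 (Protocol Table 3 and Appendix 23.4.21).

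- **Day 1 (Protocol 7.5.2.1):** "collect the aqueous humor sample before Lucentis® administration".
- **Week 4 (Protocol 7.5.2.4):** "collect the aqueous humor sample after DE-122 or Sham IVT". There is an exception: "If DE-122 or Sham IVT is not administered, the aqueous humor sample should be collected with no time restriction".
- **Week 20 (Protocol 7.5.2.8):** the same post-injection instruction, with no aqueous rule for a skipped DE-122 or Sham injection.

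The order of injections is fixed in the notes to Protocol Table 3: "Lucentis® will be administered first, and then DE-122 or Sham will be injected". A pressure check separates the two: "IOP will be measured at 40 (± 10) minutes post-injection". Neither the visit sections nor Appendix 23.4.21 gives an interval between the DE-122 or Sham injection and the aqueous sample.

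On the analysis side, Protocol 16.10.1 names serum and aqueous samples and plans changes from baseline by arm. SAP 12 states: "Scores, changes from baseline and percent change from baseline in levels of potential biomarkers will be summarized descriptively". It also plans correlations between BCVA change and each biomarker, by actual treatment and visit. SAP 4.2.2 and 4.3.4 define baseline as the last value before the first injection, which for aqueous is the Day 1 sample. SAP 5.6 defines the Biomarker Population as subjects with at least one DE-122 injection and a quantifiable post-injection serum biomarker result.

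**The concern.** A change from baseline is normally read as the response to treatment up to that visit. That reading requires baseline and follow-up values taken under the same conditions. Here the baseline eye has received no study injection, while the follow-up eye has just received one or two. A shift in an angiogenesis-related protein at Week 4 or Week 20 could come from earlier monthly doses, from the injections given at that visit, or from both.

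Evaluating biomarkers in serum and aqueous humor is a stated secondary objective (Protocol 6, SAP 2.1). A table headed change from baseline, with percent change and correlations with BCVA, would invite a reader to see a pharmacodynamic response to repeated dosing that the sampling scheme cannot isolate.

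**Working it through.** No power, alpha or sample size is involved, and the plan states no figure to reproduce. The check sets the sampling points beside the dosing schedule.

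**Dosing visits (Protocol Table 3):** Day 1 and Weeks 4, 8, 12, 16 and 20, six in all.

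| Aqueous sample | Earlier dosing visits | Injections at that visit before sampling |
|---|---|---|
| Day 1 | 0 | none |
| Week 4 | 1 | Lucentis, then DE-122 or Sham |
| Week 20 | 5 | Lucentis, then DE-122 or Sham |

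Week 4 is Day 29 ± 3, so the one earlier dosing visit lies 29 − 1 = 28 days back (25 to 31 days with the window). Lucentis precedes DE-122 or Sham by at least about 40 − 10 = 30 minutes. Where the second pressure check at 60 (± 10) minutes is needed, that check can fall as late as 60 + 10 = 70 minutes after Lucentis.

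**What the change contains.** As a simplification, treat effects as additive on the analysis scale. Let E(k) be the effect of k earlier dosing visits and A(w) the effect of the injections given at visit w. Then:

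- Week 4 − Day 1 = E(1) + A(4)
- Week 20 − Day 1 = E(5) + A(20)

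Each observed change is one number with two unknown parts. No pre-injection aqueous sample is scheduled at Week 4 or Week 20 that would separate them.

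**Does another rule in the plan cure this?** SAP 4.3.5, among the safety definitions, admits only pre-injection scores to change from baseline for measures taken both before and after injection. Aqueous has no pre-injection score at Weeks 4 and 20, so the rule yields no usable value. Serum does not have the gap: it has pre-Lucentis samples at Day 1, Week 4 and Week 20 (notes to Protocol Table 3, Appendix 23.4.20).

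**Does the arm contrast cure this?** For DE-122 minus Sham at visit w, the Lucentis part of A(w) largely cancels if sampling times are alike across arms. The DE-122 part does not. Sham does not penetrate the eye (Protocol 9.4), and the volumes injected at a visit are 50 µL in Arm 1, 50 + 20 = 70 µL in Arm 2 and 50 + 40 = 90 µL in Arm 3. The contrast is therefore E(DE-122) − E(Sham) plus a remaining same-visit difference. SAP 5.6 also requires at least one DE-122 injection, so read literally no Sham subject enters the biomarker analyses, contrary to the by-arm summary in Protocol 16.10.1.

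**Does Week 4 to Week 20 help?** Week 20 − Week 4 = [E(5) − E(1)] + [A(20) − A(4)]. The second bracket is zero only if the same-visit effect and the time to sampling are equal at the two visits. The Week 4 sample already follows the second dose, so effects before that point are lost.

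**Correlation with BCVA.** At both visits the procedures list BCVA before Lucentis, and the aqueous sample comes after the second injection. The paired values therefore lie on opposite sides of the injections.

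**The case against.** **Importance.** Aqueous sampling is optional and needs separate consent. The synopsis calls the biomarker work exploratory, the summaries are descriptive, and the trial defines no hypothesis. No efficacy or safety conclusion depends on it. All of this stands and limits the weight of the point.

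**Scores by visit are already planned.** This is true. What is missing is a label and a limit on how the change is read.

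**The Week 4 to Week 20 contrast is imperfect.** This also stands. The interval to sampling is unspecified, Protocol 7.5.2.8 allows DE-122 or Sham to be deferred within the Week 20 window, and the skipped-injection rule differs between the visits. The contrast can supplement the change from Day 1 but cannot replace it.

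**Stronger readings that the documents do not support.** A reader might infer that the change reflects only the injections given at that visit and nothing of treatment over time. That does not follow, because the samples also come after one and five earlier dosing visits. A reader might suppose that sampling occurs within an hour of injection, but no upper limit is stated. The free timing after a skipped injection might be taken to apply at both visits; it is written for Week 4 only. Lastly, the three visit sections do not contradict one another. They describe different visits, and the difficulty lies in comparing them.

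**Conclusion.** The point holds as a matter of confounding. Both scheduled post-baseline aqueous values are post-injection and the baseline is pre-injection, so the change from baseline in Protocol 16.10.1 and SAP 12 mixes the same-visit injection effect with the effect of one (Week 4) or five (Week 20) earlier dosing visits. Nothing in the SAP addresses this.

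The size of the same-visit part is unknown. The documents give neither its magnitude nor the interval from injection to sample, so it could be small or dominant. The conclusion needs only that a same-visit effect may differ from zero. A comparison with Sham would still carry a same-visit difference and, under SAP 5.6 as written, is not available at all.

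The consequence is confined to interpretation of a descriptive secondary-objective analysis in consenting subjects. Serum has pre-Lucentis samples at all three of these visits and is not affected in this way.

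**What to change.** In SAP 12:

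1. Label Week 4 and Week 20 aqueous values *post-injection* in all tables and plots.
2. State that aqueous change and percent change from Day 1, and their correlation with BCVA change, are not interpreted as a treatment effect over time.
3. Show aqueous samples from visits with a skipped DE-122 or Sham injection separately.
4. Add the Week 4 to Week 20 change as a supplementary contrast at nominally the same sampling point, noting that it starts after the second dose and misses early effects.

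In SAP 5.6, reconcile the Biomarker Population with the by-arm summary in Protocol 16.10.1 so that Sham subjects can serve as comparator.

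The cost is SAP wording, one population definition, a flag for skipped injections and one additional descriptive summary. No new data are needed, and sampling and clinical procedures are unchanged.
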